Study Process:	
1. Subjects meeting all inclusion criteria and those failing all exclusion criteria were included in the study before colonoscopy;
 
2. Include qualified novice doctors for colonoscopy training
 
3. Patients who met the requirements were enrolled and randomly assigned as follows
 
The experimental group: received painless colonoscopy training with the assistance of the artificial intelligence assistant system, which could prompt abnormal lesions and real-time withdrawal speed, and feedback the overspeed percentage.
 
Control group: routine painless enteroscopy training, no special tips.
 
4. After colonoscopy, the teacher scored the colonoscopy using ACE scoring scale

Security	Safety incidents shall be evaluated and reported according to the quality management measures for clinical trials of medical devices

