#### 3.1 Endoscopic physician

➤ Inclusion criteria

Novice colonoscopists without previous experience in independent colonoscopy;

➤ Exclusion criteria

- 1) The number of operating cases does not meet the requirement of sample size
- 2) could not provide informed consent

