## **4 Endpoints**

### **4.1 Primary Endpoint**

- 1) CUSUM learning curve for colonoscopy (ACE scoring scale)
- 2) Average test score difference before and after training

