### **4.2 Secondary Endpoints**

- 1) Detection rate of advanced adenoma: the numerator is the number of patients diagnosed with advanced adenomas, and the denominator is the total number of patients undergoing colonoscopy, Advanced adenoma was defined as > 10mm adenoma, villous adenoma, tubular villous adenoma, high-grade intraepithelial neoplasia, and carcinoma.

- 2) Polyp Detection Rate, PDR: the numerator is the number of patients with polyps detected by colonoscopy, and the denominator is the total number of patients who underwent colonoscopy
- 3) Average number of adenomas detected per patient: the numerator is the total number of adenomas detected by colonoscopy, and the denominator is the total number of patients undergoing colonoscopy.
- 4) The detection rate of large, small and micro polyps: the numerator is the number of patients with large ( $\geq 10$  mm), small (6-9 mm) and micro-small ( $\leq 5$  mm) polyps detected by colonoscopy, and the denominator is the total number of patients receiving colonoscopy.
- 5) The average number of large, small and micro polyps detected: the numerator is the total number of large ( $\geq 10$  mm), small (6-9 mm) and micro-small ( $\leq 5$  mm) polyps detected by colonoscopy, and denominator is the total number of patients undergoing colonoscopy.
- 6) The detection rate of large, small and micro adenomas: the numerator is the number of patients with large ( $\geq 10$  mm), small (6-9 mm) and micro-small ( $\leq 5$  mm) adenomas detected by colonoscopy, and the denominator is the total number of patients receiving colonoscopy.
- 7) The average number of large, small and micro adenomas detected: the numerator is the total number of large ( $\geq 10$  mm), small (6-9 mm) and micro-small ( $\leq 5$  mm) adenomas detected by colonoscopy, and denominator is the total number of patients undergoing colonoscopy.
- 8) The detection rate of adenoma in different sites: the numerator is the number of patients with adenomas detected in the rectum, sigmoid colon, descending colon, transverse colon, ascending colon, ileocecal region and other sites during colonoscopy, and the denominator is the total number of patients receiving colonoscopy.

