- 9) The average number of adenomas detected in different sites: the numerator is the total number of adenomas detected in the rectum, sigmoid colon, descending colon, transverse colon, ascending colon, ileocecal region and other sites during colonoscopy, and the denominator is the total number of patients undergoing colonoscopy.
- 10) Number of missed return of the sliding endoscopy/number of successful return of the sliding endoscopy: the numerator is the total number of sliding endoscopy during colonoscopy, and the denominator is the number of sliding endoscopy and successful return endoscopy during colonoscopy
- 11) Real-time gut cleanliness score: during colonoscopy, a real-time intestinal cleanliness score was given by EndoAngel based on the Boston-scale Boreal Preparation Score (BBPS).

- 12) withdraw overspeed percentage:the ratio of the overspeed duration to the total duration in the process of withdrawal.
- 13) The withdraw time:the time between colonoscopy arrival at ileocecal valve and colonoscopy exit from anus.
- 14) Ratio of ileocecal reach:for a period of time, the number of colonoscopies that failed to reach the ileocecal part accounted for the proportion of the total number of colonoscopies.

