### **6.3.4 Post-operative Managements**

[figure not shown]
- 1) Postoperative routine nursing
- 2) The anesthetized subjects were observed until they woke up
- 3) Patients with no lesions such as polyps were followed up until they woke up and left

the endoscopic room.

- 4) Clinical information such as the examining physician, duration of examination, sedation status, whether to ileocecal reach, bowel readiness, complications, polyp characteristics (number, location, size, color, and shape), and pathological results will be collected and recorded in a Web-based data management system.
- 5) The images and video data were collected for the functional evaluation of EndoAngel, such as the withdrawal speed, the number of sliding not returned/sliding returned, real-time intestinal preparation score, polyp detection and typing, etc.

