## 8.2 Methods

Continuous variables should be described by number of subjects, mean, standard deviation, median, minimum and maximum. The classification variables are summarized by frequency and percentage.

Spearman rank correlation analysis was used to analyze the correlation between endoscopic overspeed percentage / intestinal preparation score and adenoma detection rate / advanced adenoma detection rate / polyp detection rate.

Univariate analysis was used to analyze the correlation between the number of unreturned slides/returned slides and the detection rate of adenoma/late adenoma/polyp.

Chi-square analysis was used to analyze the detection rate of adenomas in different scores of intestinal segments.

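### Section 8.2 correlates overspeed and slide returns with lesion detection without adjustment, so a crude case-level result could reflect the trainee's stage of training or the trial arm rather than technique.

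*Combined protocol and SAP*

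**What the plan says.** Section 8.2 Methods of the combined protocol and SAP names two analyses that link technique to detection.

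- For overspeed: "Spearman rank correlation analysis was used to analyze the correlation between endoscopic overspeed percentage / intestinal preparation score and adenoma detection rate". The sentence goes on to advanced adenoma and polyp detection.
- For slide returns: "Univariate analysis was used to analyze the correlation between the number of unreturned slides/returned slides and the detection rate of adenoma/late adenoma/polyp".

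Neither names a covariate, and the word univariate rules one out for slide returns. No other section adds case number, trainee, arm or centre to these analyses. Section 8.2 does not state the unit of analysis either. Section 4.2 defines overspeed within one withdrawal ("the ratio of the overspeed duration to the total duration in the process of withdrawal") and detection rates over patients (for polyps, "the numerator is the number of patients with polyps detected by colonoscopy"), which points to the single colonoscopy.

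Three other places bear on the point.

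- Section 3.1 admits as operators "Novice colonoscopists without previous experience in independent colonoscopy", and the first primary endpoint in 4.1 is a CUSUM learning curve of the ACE score. Case order enters the plan only there.
- The study process in section 1 gives the experimental group a system "which could prompt abnormal lesions and real-time withdrawal speed, and feedback the overspeed percentage".
- Section 6.3.4 records "Clinical information such as the examining physician, duration of examination, sedation status" among other items, and 6.5.1 records the randomisation time to the minute.

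**The concern.** The trial is built on the idea that novices change over consecutive cases. If overspeed and missed returns fall with practice while detection rises, early cases combine poor technique with few lesions found and late cases the reverse. Pooling them produces a correlation even when, at any given stage of training, technique in a case has no bearing on detection in that case. This can happen within one arm and one trainee, so terms for arm and trainee alone would not remove it.

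Arm is a second, separate route. The system prompts on withdrawal speed and on lesions, so the experimental group can have both less overspeed and more detection without one producing the other. Allocation in blocks of four should keep the arms roughly balanced over calendar time, so a case-number term would not remove the arm effect.

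Both routes push in the direction that looks favourable: less overspeed with more lesions found. A significant crude result could not separate slower withdrawal going with more detection from a later case or an AI-assisted one.

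**Working it through.** **Plan's own figures.** Section 8.3 takes 350 cases for the motor score and adds 10%: 350 × 1.10 = 385, which reproduces the stated total. The documents give no figure for the 8.2 correlations, so their behaviour has to be examined under assumptions.

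**Assumed, not in the documents.** Number of trainees (6 to 20), SD of overspeed at a given case number (12 percentage points), linear trends over training, and slide counts (Poisson, starting mean 3). In every learning scenario the true link at a given case number is zero, and there is no arm effect.

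**Formula.** Let t be the position in training, uniform on 0 to 1, with SD 1/√12. If overspeed and detection are independent given t, their crude correlation has size about corr(overspeed, t) × corr(detection, t), where

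- corr(overspeed, t) = (Δo/√12) / √(12² + (Δo/√12)²), with Δo the change in percentage points;
- corr(detection, t) = (Δd/√12) / √(p(1−p)), with Δd the change in detection and p its mean.

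With z = r√(n−1), the two-sided 5% test rejects with probability P(Z > 1.96 − z) + P(Z < −1.96 − z).

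**Overspeed against polyp detection, n = 385.**

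| Assumed change | Product | Size of r | z | Rejection by formula | Simulated (6 / 12 trainees) | Simulated, case number partialled out |
|---|---|---|---|---|---|---|
| Overspeed 30→22%, detection 35→45% | 0.189 × 0.059 | 0.011 | 0.22 | 5.6% | 5.7 / 5.3% | 4.7 / 5.0% |
| Overspeed 30→15%, detection 30→50% | 0.339 × 0.118 | 0.040 | 0.78 | 12.3% | 12.8 / 12.8% | 5.2 / 4.8% |
| Overspeed 40→15%, detection 25→60% | 0.515 × 0.204 | 0.105 | 2.06 | 54% | 54.5 / 57.9% | 5.0 / 4.6% |

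The sign is negative throughout. For the middle row, (15/3.464)/√(144 + 18.75) = 4.330/12.757 = 0.339, and (0.20/3.464)/√0.24 = 0.0577/0.490 = 0.118.

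**Second set of scenarios, 350 cases, 10 trainees, overspeed and slide returns.**

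| Assumed change | Mean rho, overspeed | False positives, overspeed | False positives, slide returns |
|---|---|---|---|
| Overspeed 40→30%, detection 30→35% | −0.01 | 4% | 4% |
| Overspeed 40→30%, detection 25→40% | −0.02 | 7% | 6% |
| Overspeed 40→20%, detection 25→40% | −0.04 | 14% | 8% |
| Overspeed 40→20%, detection 20→45% | −0.07 | 26% | 12% |

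With 6 or 20 trainees the third row gives 12% for overspeed and 7-8% for slide returns. With case number in the model, both measures return to 4-6% in every row. If overspeed does not trend, there is no inflation.

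**Unit of analysis, same four rows.** With rates per trainee per five-case block, false positives for overspeed run from 6% to 55% (mean rho −0.04 to −0.25). With one average per trainee and equal case counts the shared trend cancels: rho about 0, false positives about 5-6%.

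**Arm alone, no learning, 175 cases per arm.** Here the SD of the shared factor is 1/2 rather than 1/√12. Overspeed 40% against 25% with detection 25% against 35% gives (7.5/√(144 + 56.25)) × (0.05/√0.21) = 0.530 × 0.109 = 0.058, z = 1.08, rejection 19%; simulation gave 19%. Overspeed 40% against 20% with detection 25% against 40% gives 0.640 × 0.160 = 0.102, z = 1.91, rejection 48%; simulation gave 50%.

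**The case against.** The strongest reply is that these are peripheral analyses. Section 8.3 puts the main evaluation focus on ACE scores. The technique-detection correlations are not among the endpoints in 4.1 or 4.2, and nothing ties them to the sample size or to a decision. Section 8.2 plans only to describe a correlation and claims no causal or stage-specific link; a crude correlation labelled as such is not an error. This stands, and it limits the weight of the point.

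The shared trend is also assumed. The only learning curve in the plan is for the ACE score. No section says that overspeed, slide returns and detection all move with practice, and 6.3.3 has trainees work under a teacher, which could flatten a detection trend. The largest rates need polyp detection to go from 25% to 60% within about 64 cases per trainee (385/6) or 32 (385/12), and even then rho is only about −0.11. That stands too.

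Two stronger readings are tempting. A reader might infer that the trial will report a false technique-detection link. The documents do not support this: they give no trends, and lack of independent experience does not show that trial cases begin with a trainee's first examination. A reader might also infer that the trial's main result is compromised. It is not, because the randomised comparison of ACE scores does not use these correlations.

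What survives is that, at case level, the planned methods cannot tell technique from training stage or arm, although the operator and a time stamp are already recorded.

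**Conclusion.** The omission is certain from section 8.2; its consequence is conditional. With the individual colonoscopy as the unit and trends of the assumed sizes, the false-positive rate for overspeed runs from about 5% with slight learning, through 12-26% with moderate learning, to above 50% with marked learning. For slide returns it is 4-12%. Arm alone can give 19-50% for overspeed. Learning produces no inflation if the unit is the trainee with equal case counts.

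These figures rest on assumed trends, spread and trainee numbers. Detection was simulated as a single yes/no outcome, so adenoma and advanced adenoma were not examined separately. The return to about 5% was shown for case number with no arm effect; the joint adjustment below follows from the same reasoning but was not simulated, nor was the bowel preparation term. This is a worthwhile, cheap improvement to a supporting analysis, not a defect in the primary comparison.

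**What to change.** In section 8.2:

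1. State that the unit of analysis is the individual colonoscopy.
2. Replace the two-variable analyses of overspeed and slide returns with a regression of detection (yes/no) on the measure. Include case number within trainee, arm, trainee (fixed or random effect) and the bowel preparation score of the same case, which 8.2 already relates to detection.
3. Derive case number from the examining physician (6.3.4) and the order of examinations. Randomisation time (6.5.1) can serve as a proxy. Note that it precedes the examination and counts enrolled cases only, so any other procedures a trainee performs are missed.
4. Interpret the adjusted result and report the crude correlation as description.

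The cost is a short rewording and one variable derived from data already recorded. A few degrees of freedom are lost, more if trainee is a fixed effect and trainees are many. The adjusted estimate describes the link at a given level of experience and within arm, which is a narrower question than the crude correlation; the text should say so.

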##### 6.4.2 Intraprocedure

For safety reasons, the investigator may have the subject quit during the procedure. For example, the patient is not suitable for receiving the instrument for the study or the endoscopists do not use the specified instrument for any reason. If the following serious

cases occur, please withdraw during the operation:

- a) perforation
- b) bleeding
- c) allergy to narcotic drugs
- d) Intestinal cleanliness is very poor, endoscopic physicians can not smoothly advance: a single intestinal segment is less than 1 point
- e) can not complete colonoscopy due to obstruction, intolerance, inflammatory bowel disease or colorectal resection
- f) can not biopsy due to coagulation dysfunction or oral anticoagulants

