### 8.3 Sample Size Calculation

The main evaluation focus of this project plan is to evaluate whether there is a significant difference in ACE scores of colonoscopy training for endoscopic physicians by using EndoAngel. This project plans to carry out clinical trials in 3 hospitals. According to the literature, we assume that the cognitive score of endoscopists can be increased from 2.5 to 2.8 after intervention, then 126 cases of colonoscopy need to be enrolled, and if the motor score of endoscopists is increased from 2.38 to 2.59, then 350 cases need to be enrolled. Considering the experimental abscission rate of 10%, a total of 385 cases of colonoscopy should be included.

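### Section 8.2 does not state the unit of its chi-square test of adenoma detection by segment score; if segments are pooled, p-values are probably too small

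*Combined protocol and SAP*

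**What the plan says.** Section 8.2 (Methods) names three inferential analyses, and the third is a single sentence: "Chi-square analysis was used to analyze the detection rate of adenomas in different scores of intestinal segments". It does not say whether the observation is a segment or a patient, whether segments are combined in one table, or how several segments from one patient are handled. No clustered method appears anywhere in section 8.

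Three other places bear on the reading:

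- Section 4.2, item 11, defines the cleanliness measure: "a real-time intestinal cleanliness score was given by EndoAngel based on the Boston-scale". Section 6.4.2 (Intraprocedure) shows that scores exist for individual segments, since one of its criteria is that "a single intestinal segment is less than 1 point".
- Section 4.2, item 8, records adenomas at several sites in each patient, "rectum, sigmoid colon, descending colon, transverse colon, ascending colon, ileocecal region and other sites". For that site-specific rate, "the denominator is the total number of patients receiving colonoscopy".
- Section 8.3 puts the main focus elsewhere, namely to "evaluate whether there is a significant difference in ACE scores of colonoscopy training".

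**The concern.** Pearson's chi-square assumes independent observations. Segments from one patient share one bowel preparation and one underlying adenoma risk, so both the score and the presence of an adenoma can be expected to resemble each other within a patient. If each segment enters one table as a separate observation, the table treats the data as more informative than they are.

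What is at stake is a false claim that segment cleanliness is associated with adenoma detection. Because the sentence leaves the unit open, the simplest implementation (one pooled score-by-detection table) is also the one exposed to this error.

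**Working it through.** **1. Which analysis is described?** Section 8.2 already relates the overall preparation score to detection rates by Spearman correlation. The chi-square sentence refers instead to scores of segments, and section 6.4.2 (Intraprocedure) confirms that such scores exist. A segment-level comparison is therefore the most natural reading, though not the only one.

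**2. Is there a plan figure to reproduce?** No. The documents give no alpha, power, segment count, detection rate or within-patient correlation for this test. The total of 385 (350 × 1.10) comes from the ACE scores and has no bearing here.

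**3. Analytic size of the effect.** With m segments per patient and no true association, the variance of a 1-df score statistic is inflated by

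DE = 1 + (m − 1) × ICC(score) × ICC(detection),

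and the actual two-sided error at a nominal 5% is 2 × [1 − Φ(1.96/√DE)]. Both ICCs must be non-zero for DE to differ from 1. Two assumed examples:

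- m = 3, ICCs 0.5 and 0.1: DE = 1 + 2 × 0.5 × 0.1 = 1.10, error 0.062.
- m = 6, ICCs 0.8 and 0.3: DE = 1 + 5 × 0.8 × 0.3 = 2.2, error 0.186.

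**4. Simulation of the pooled Pearson test with no true association.** All inputs except the patient number are assumptions:

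- 350 patients (section 8.3, before the dropout allowance)
- m = 3 or 6 segments (six matches the named sites in section 4.2, item 8, but nothing says cleanliness is scored at each)
- 15% of segments with an adenoma
- a four-level score with probabilities 0.05, 0.15, 0.45 and 0.35, or a two-level score with probabilities 0.2 and 0.8
- latent-normal within-patient correlations
- 4,000 runs per setting, so the Monte Carlo standard error near 5% is √(0.05 × 0.95/4000) = 0.003

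| Latent correlation, score / detection | m = 3, four-level | m = 3, two-level | m = 6, four-level | m = 6, two-level |
|---|---|---|---|---|
| 0 / 0 | 0.042 | 0.050 | 0.050 | 0.046 |
| 0 / 0.3 | 0.050 | 0.050 | 0.049 | 0.052 |
| −0.15 / 0.4 | 0.047 | 0.041 | 0.045 | 0.045 |
| 0.5 / 0.2 | 0.051 | 0.058 | 0.058 | 0.065 |
| 0.5 / 0.4 | 0.069 | 0.062 | 0.093 | 0.080 |
| 0.8 / 0.3 | 0.075 | 0.066 | 0.117 | 0.104 |
| 0.8 / 0.5 | 0.102 | 0.076 | 0.184 | 0.136 |

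A boundary case with almost identical scores across a patient's segments (0.99 / 0.5, four-level) gives 0.157 for m = 3 and 0.326 for m = 6. The 0.8 / 0.5 row is therefore not an upper limit.

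**5. Second simulation with other assumed inputs.** With 385 patients, 12% of segments with an adenoma, a three-level score, latent correlations from 0.5 / 0.2 to 0.7 / 0.6 and 3,000 runs per setting, the error is 0.065–0.102 for three segments and 0.065–0.159 for six. The direction and the upper figures agree with step 4. The lower end differs (0.065 against 0.051 for three segments), so it depends on the assumed inputs.

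**6. One segment per patient in each test.** The simulated error is 0.047 (four-level) and 0.049 (two-level), so there is no inflation.

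**The case against.** The strongest objection is that pooling is not in the documents. Testing each segment separately also fits the sentence in section 8.2, and the one site-specific adenoma detection rate that the plan defines (section 4.2, item 8) has patients as its denominator. On that reading each patient contributes one observation per test and the within-patient problem disappears. This stands as a reason to make the point conditional. It does not remove the point, because item 8 defines a rate by site and not the comparison across scores, so it does not show that separate tests are planned.

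A reader might go further and infer that the test is simply invalid and its error rate certainly above 5%. The documents do not support that. Inflation needs pooling and also within-patient correlation of the same sign in both score and detection. With an uncorrelated score there is none, and with modest correlation and three segments it can be negligible.

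A reader might also infer further inflation because patients are nested within trainees. The design makes such clustering possible, but the number of trainees is not stated and none of the calculations covers it, so no size can be claimed.

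Finally, it might be inferred that the trial's conclusion is at risk. It is not: this analysis does not compare the arms, is not a listed endpoint, and plays no part in the ACE comparison or the sample size.

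**Conclusion.** The point holds in conditional form. Section 8.2 leaves the unit of analysis unstated and makes no allowance for several segments per patient. If segments are pooled, as the wording most naturally suggests, independence fails and the p-values are probably too small.

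Over positive latent correlations of 0.5–0.8 for score and 0.2–0.6 for detection, type I error ranges from about 5% to about 10% with three segments. With six segments it ranges from about 6% to 16–18%. The correlations, segment counts, detection rates and score distributions are all assumptions, and the direction rests on both correlations being positive. If each segment is tested separately, there is no within-patient inflation. The consequence is minor and confined to one secondary association.

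**What to change.** State the unit of analysis in section 8.2 and choose one of two routes:

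- **Segments pooled.** Name the segment as the unit and replace the Pearson chi-square with a patient-clustered method. One choice is a logistic GEE of segment-level adenoma detection on segment score, with robust standard errors, segment location as a covariate, and odds ratios with 95% confidence intervals. Location belongs in the model because cleanliness and adenoma frequency may both vary along the bowel. A Rao-Scott chi-square clustered by patient is the simpler alternative. Adjustment for arm and trainee is optional.
- **Segments tested separately.** Say so, list the segments, and state how the resulting set of p-values will be read, since section 8.2 gives no multiplicity rule.

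The cost is one or two sentences of text and, for the clustered route, a few lines of code and slightly wider intervals. No new data are needed and the sample size does not change.

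### The chi-square of adenoma detection by segment cleanliness score does not say whether segments are pooled; if they are, it can confuse bowel location with cleanliness (low priority, exploratory)

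*Combined protocol and SAP*

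**What the plan says.** Section 8.2 (Methods) ends with the sentence "Chi-square analysis was used to analyze the detection rate of adenomas in different scores of intestinal segments". It gives no unit of analysis, table layout, score categories, stratification or adjustment, and none is added elsewhere.

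These places bear on how to read it:

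- **Scores by segment.** Section 6.4.2 (Intraprocedure) withdraws a patient when "a single intestinal segment is less than 1 point", so scores exist at segment level at least there and in the section 8.2 sentence. Section 4.2 item 11 defines the EndoAngel cleanliness score without mentioning segments.
- **Adenomas by site.** Section 4.2 item 8 is "The detection rate of adenoma in different sites". It lists six named sites plus others, and for each "the denominator is the total number of patients receiving colonoscopy". Section 6.3.4 says that polyp location is recorded.
- **A neighbouring analysis.** Section 8.2 also plans the following: "Spearman rank correlation analysis was used to analyze the correlation between endoscopic overspeed percentage / intestinal preparation score and adenoma detection rate". It makes no reference to segment.

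**The concern.** The useful question is whether, in a given part of the bowel, adenomas are found less often when that part is less clean. A table that stacks all segments and groups them by score answers a different question: whether detection and score are related once locations are mixed. If some segments tend to be dirtier and also carry more (or fewer) adenomas, the low-score and high-score groups hold different mixes of locations. A significant result might then reflect only where adenomas occur, and a null result might mask a real loss of detection in poorly cleaned bowel.

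This is separate from the fact that several segments come from one patient. Allowing for clustering corrects the standard error but leaves the location effect in the estimate.

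**Working it through.** **Figure to reproduce.** None. The sentence states no rate, alpha, power or sample size. The trial total of 385 (350 x 1.10, section 8.3) is used only to set a realistic scale.

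**When pooling misleads.** Suppose there is no cleanliness effect within any segment. Let a_s be the adenoma rate in segment s and c_s the proportion of patients whose segment s scores high. With equal numbers per segment, the pooled rates are

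- high score: sum(a_s c_s) / sum(c_s)
- low score: sum(a_s (1 - c_s)) / sum(1 - c_s)

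Their difference is Cov(a, c) / [c̄(1 - c̄)], with the covariance taken across segments. It is zero if a_s or c_s is constant. Bias therefore needs both to differ, and to vary together.

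**Hand check.** Assumed inputs: 3 segments, 350 patients, two score levels, independent segments.

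*Moderate:* a = 15/8/12%, c = 50/75/65%.
- High: (0.075 + 0.060 + 0.078)/1.90 = 0.213/1.90 = 11.2%
- Low: (0.075 + 0.020 + 0.042)/1.10 = 0.137/1.10 = 12.5%
- Spurious odds ratio: (0.213/1.687)/(0.137/0.963) = 0.89
- Overall rate 0.35/3 = 0.1167; group sizes 665 and 385; SE = sqrt(0.1167 x 0.8833 x (1/665 + 1/385)) = 0.0206
- z = 0.0124/0.0206 = 0.61, so rejection at two-sided 5% is about 9%

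*Strong:* a = 20/6/12%, c = 40/80/65%.
- High: 0.206/1.85 = 11.1%; low: 0.174/1.15 = 15.1%
- Spurious odds ratio: (0.206/1.644)/(0.174/0.976) = 0.70
- SE 0.0211, z = 1.89, rejection about 47%

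**Simulation of the same two-level design** (3,000 runs). CMH is the Cochran-Mantel-Haenszel test stratified by segment.

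| Assumed scenario | False positives, pooled | False positives, CMH | Power at true OR 1.5, pooled | Power at true OR 1.5, CMH |
|---|---|---|---|---|
| Only adenoma rate differs | 4.0% | 4.1% | 59% | 60% |
| Only score differs | 5.2% | 4.8% | 62% | 61% |
| Both moderate, opposite directions | 10.2% | 4.5% | 32% | 56% |
| Both moderate, same direction (8/10/16%; 50/65/75%) | 10.2% | 5.0% | 81% | 51% |
| Both strong, opposite directions | 47.4% | 5.0% | 6% | 57% |

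The hand figures agree with the simulated ones. The 81% is not extra power: the median pooled odds ratio there is 1.71 for a true 1.5.

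**Three score levels** (assumed scores 1-3, 385 patients x 3 independent segments, 2-df tests). Pooled false positives are:

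- 5-7% with a small score difference (segment means 2.08 v 2.24)
- 5-12% with a moderate one (1.97/2.28/2.28)
- 7-25% with a large one (1.85/2.35/2.35)

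The stratified test stays at 4.1-5.4%. For a true odds ratio of 1.5 per point with the dirtier segment richer in adenomas, power is 51-58% pooled v 77-83% stratified (moderate), and 35-43% v 74-79% (large). With the dirtier segment poorer in adenomas (moderate), pooling rejects 95% v 80%. A repeat run gave similar values, for example 10.7% v 4.8% false positives (moderate) and 23.6% v 5.5% (large).

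**Dependence.** Those stratified error rates rely on independent segments. With assumed within-patient latent correlation, ordinary CMH rejected 5-6% under the null when correlation was mild (0.3 for adenoma, 0.5 for score). It rejected 9-10% when correlation was strong (0.5 and 0.7-0.9). Stratifying alone is therefore not enough.

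**The case against.** The strongest reply is that the plan never says it pools. One chi-square table per segment also fits the sentence, and then location cannot confound the result. That stands: a reader might infer that the planned test is confounded as written, and the text supports only that it is unspecified and may be run that way.

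A reader might also take the by-site endpoints as evidence that adenoma rates differ by site. Section 4.2 gives no reason for reporting by site, and no rate or score distribution by segment appears anywhere. The conditions for bias are plausible but undocumented, and every size above is assumed.

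Third, section 8.2 states no hypothesis, so the within-segment question is the reviewer's reading of the purpose. Stratifying would not make the result attributable to cleanliness either, because trainee, withdrawal and patient factors remain.

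Finally, the stakes are small. Section 8.3 puts the main focus on ACE scores; this association is not a listed endpoint and does not drive the sample size.

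What survives is that an analyst could follow the sentence and run the pooled table, and that a clearer analysis is cheap.

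**Conclusion.** The point holds in conditional form. Section 8.2 plans an unstratified chi-square and leaves pooling open. If segments are pooled, and adenoma rate and score both differ by segment and vary together, the test mixes location with cleanliness. The distortion ranges from negligible to serious, depending on assumed inputs that the documents cannot confirm or exclude. It disappears if either quantity is equal across segments or if each segment is tested separately.

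Priority is low. The analysis is exploratory and compares no arms, and an error in it would not change the primary conclusion.

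**What to change.** Replace the last sentence of section 8.2 with a segment-level analysis:

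- Fit a logistic model of adenoma found in a segment on that segment's cleanliness score, with segment as a factor.
- Use standard errors that allow for clustering by patient and, where feasible, by trainee, for example through GEE. The documents do not give the number of trainees, so the SAP should say how this is handled if there are few.
- Report the within-segment odds ratio per score point with its 95% CI, and show the score-by-detection table for each segment.
- Define how recorded polyp sites map to scored segments, and confirm that segment-level scores are stored. Section 6.3.4 lists polyp location but only a real-time preparation score.
- Do not interpret a table pooled over segments, and state that the model removes confounding by location only.

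**Cost.** SAP wording, a mapping table and a few lines of code, with no new data if segment scores are kept. If segments do not differ, stratifying cost 0-5 points of power in one simulation and 3-6 in the repeat. Those figures are for a 2-df stratified test, not for the per-point model, so treat them as a rough guide.
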